8.2 Unscheduled Visits

When necessary, unscheduled visits may be conducted, in particular if an AE occurs and needs to be assessed and/or treated.

 GALDERMA	Title 43QMI902 Clinical Study Protocol - QM1114 - LCL and GL	Doc id MA-40371
--	---	----------------------------------

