1.5.6 Electrocardiogram (ECG)

ECG recordings will be done at baseline (before treatment), Month 1 and Month 6. The following items will be measured:

- RR interval
- PR interval
- QRS interval
- QT interval
- Heart rate (HR)
- QTcB interval
- QTcF interval

 GALDERMA	<small>Title</small> 43QMI902 Statistical Analysis Plan US - QMI114-DP - GL&LCL	<small>Doc id</small> MA-43265
---	--	-----------------------------------

Effective date: 2021-02-05 13:16

Effective

Version: 1.0

During each visit where ECG is conducted, the ECG will be recorded in triplicates. In addition to the individual measurements the above items will be aggregated into a mean value per visit (mean of all beats). ECG endpoints include:

- Aggregated values collected at each visit
- Changes from baseline
- QTcB and QTcF prolongation criteria
- Overall assessment (Normal, Abnormal Not Clinically Significant, Abnormal Clinically Significant) of the ECG

 GALDERMA	Title 43QMI902 Statistical Analysis Plan US - QM1114-DP - GL&LCL	Doc id MA-43265
--	---	----------------------------------

Effective date: 2021-02-05 13:16

Effective

Version: 1.0

2 Statistical Methods

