2.1.1 Visit windows

Study visits are expected to occur according to the protocol schedule in [Appendix F](#). All data will be tabulated per the evaluation visit as recorded on the eCRF even if the assessment is outside of the visit window. In data listings, the relative study day (in relation to date of study drug administration) of all dates will be presented. There will not be any windowing for unscheduled visits in the analysis, and unscheduled visits will not be included in any analyses. Unscheduled visits, if any, will be presented in listings only.

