2.5.5 Physical examinations and vital signs

The number and percentage of subjects with normal/abnormal results in physical examination will be presented by visit and treatment. A shift table will be created to present any change from

	Title 43QMI1902 Statistical Analysis Plan US - QM1114-DP - GL&LCL	Doc id MA-43265
--	--	----------------------------------

baseline in normal/abnormal results in physical examination across the study visits for each treatment group.

Vital signs at baseline, Day 7, Day 14, Month 1 and Month 6, and the changes from baseline will be summarized by treatment and visit using descriptive statistics.

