2.5.6 ECG

The aggregated value of each ECG measurement (described in [Section 1.5.6](#)) at baseline, Month 1, Month 6, and the changes from baseline will be summarized descriptively by treatment group at each visit. In addition, a shift table will be created to show any change from baseline to Month 6 in the overall ECG assessment.

QTcF and QTcB interval prolongation will be presented separately as well. The number and percentage of subjects with a QTcF and/or QTcB interval of >450 msec, >480 msec, and >500 msec will be summarized by treatment and visit, along with the number and percentage of subjects with a change from baseline in QTcF and/or QTcB interval of $30 - < 60$ msec and ≥ 60 msec.

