	Product or Injection Procedure by System Organ Class and Preferred Term		
14.3.7 – 14.3.12 Other Safety			
14.3.7.1	Local Spread of Toxin Events by Intensity, MedDRA System Organ Class and Preferred Term	Safety	U
14.3.7.2	Remote Spread of Toxin Events by Intensity, MedDRA System Organ Class and Preferred Term	Safety	R
14.3.7.3	Hypersensitivity Events by Intensity, MedDRA System Organ Class and Preferred Term	Safety	R
14.3.8	Summary of Hematology Parameters and the Change from Baseline	Safety	U
14.3.9	Summary of Chemistry Parameters and the Change from Baseline	Safety	R
14.3.10	Summary of Vital Sign Parameters and the Change from Baseline	Safety	U
14.3.11	Shift from Baseline in Physical Examination	Safety	U
14.3.12.1	Summary of Electrocardiogram (ECG) Results at Each Visit	Safety	U
14.3.12.2	Electrocardiogram (ECG) Overall Assessment – Shift from Baseline to Each Study Visit	Safety	U
14.3.12.3	Number and Percentage of Subjects with Post-Baseline Abnormal Electrocardiogram (ECG) Results	Safety	U

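### SAP 2.1.1 keeps unscheduled visits out of every analysis, so safety readings taken there and not judged clinically significant are counted in no by-arm table

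*SAP*

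**What the plan says.** **The rule.** SAP 2.1.1 states that "unscheduled visits will not be included in any analyses. Unscheduled visits, if any, will be presented in listings only". SAP 2.5 and its subsections on laboratory data, physical examination, vital signs and ECG add no exception for safety. The safety analysis section of the protocol (9.1.3.2) contains no such exclusion.

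**When these visits happen.** Protocol 8.2: "When necessary, unscheduled visits may be conducted, in particular if an AE occurs and needs to be assessed and/or treated". It does not list tests to be done.

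**The tables affected.**
- ECG: "ECG recordings will be done at baseline (before treatment), Month 1 and Month 6" (SAP 1.5.6). Under SAP 2.5.6 the QTc categories are tabulated per visit: ">480 msec, and >500 msec will be summarized by treatment and visit". Changes of 30 to <60 and of at least 60 msec are counted in the same table. For the overall reading, "a shift table will be created to show any change from baseline to Month 6 in the overall ECG assessment"; the title of Table 14.3.12.2 extends this to each study visit. Table 14.3.12.3 exists only as a title: "Number and Percentage of Subjects with Post-Baseline Abnormal Electrocardiogram (ECG) Results".
- Focused physical examination (FPE) and vital signs are summarised by visit, with a shift table for FPE (SAP 2.5.5).
- Laboratory data are summarised at Day 0 and Month 6 (SAP 2.5.3).

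**The AE route.** FPE abnormalities found after injection are to be recorded as AEs (Protocol 7.2.1, Appendix 6). So are clinically significant changes in vital signs (7.2.2) and ECG (7.2.3), and clinically significant laboratory values that are new or worsened (7.2.4, SAP 2.5.3). SAP 4.2 plans listings for all of these data types.

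**The concern.** Leaving irregular visits out of by-visit means is ordinary practice. Leaving them out of counts of abnormal findings is different, because here the visit can be prompted by the event. Those who come in unscheduled are, in part, subjects with something to investigate, so the excluded readings are not a random subset.

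The AE tables cover what the investigator judges clinically significant. Threshold counts have a separate purpose: they show by arm how often a fixed limit was crossed, without relying on that judgement. Under the rule as written they do this only for scheduled visits. At stake are the completeness of the ECG, laboratory and vital-sign endpoints as tabulated by arm, and agreement between the ECG and FPE tables and the AE tables. No efficacy result is touched.

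**Working it through.** The plan gives no figure to reproduce. The check is textual, followed by a scale for one subject.

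**1. Where does a post-treatment reading from an unscheduled visit go?**

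| Reading | ECG, FPE, laboratory or vital-sign table | AE table | Listing |
|---|---|---|---|
| Any FPE abnormality | No | Yes (Protocol 7.2.1) | Yes |
| ECG or vital-sign change judged clinically significant | No | Yes (7.2.2, 7.2.3) | Yes |
| Laboratory value judged clinically significant, new or worsened | No | Yes (7.2.4) | Yes |
| ECG abnormal, not judged clinically significant | No | No | Yes |
| QTcF or QTcB above 450, 480 or 500 msec, or change of at least 60 msec, not judged clinically significant | No | No | Yes |
| Laboratory or vital-sign value out of range, not judged clinically significant | No | No | Yes |

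The last three rows have no by-arm count anywhere. The fourth is a category that SAP 1.5.6 itself defines as an ECG outcome.

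**2. Can the tables disagree?** Yes. A subject with a normal FPE at every scheduled visit and an eyelid finding at an unscheduled one has an AE, while the FPE shift table shows no abnormality. The same can happen between the AE tables and either the ECG shift table or Table 14.3.12.3, although that table's title suggests any post-baseline ECG.

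**3. Does the schedule compensate?** Only partly. With 1 month = 28 days (Protocol Table 2), Month 1 is Day 28 and Month 6 is Day 168.
- Laboratory: nothing scheduled between Day 0 and Day 168.
- ECG, FPE and vital signs: nothing scheduled between Day 28 and Day 168, a nominal gap of 168 − 28 = 140 days.

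Early-termination readings (Month 6/ET) and out-of-window readings kept under their eCRF visit can fall inside these gaps and are analysed. A reading recorded as unscheduled is not.

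**4. Scale.** Planned arm sizes are 118 (each active arm) and 59 (placebo). One subject adds 100/118 = 0.85 percentage points in an active arm and 100/59 = 1.69 in placebo.

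Let p be the proportion of subjects whose only crossing is at an unscheduled visit and is not recorded as an AE. The documents do not give p, so the values below are assumptions. Expected number missed = n × p; chance of at least one = 1 − (1 − p)^n.

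| Assumed p | Active arm: expected, chance of ≥1 | Placebo: expected, chance of ≥1 |
|---|---|---|
| 0 | 0, 0% | 0, 0% |
| 0.5% | 0.6, 45% | 0.3, 26% |
| 1% | 1.2, 70% | 0.6, 45% |
| 2% | 2.4, 91% | 1.2, 70% |
| 5% | 5.9, 99.8% | 3.0, 95% |

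**The case against.** The strongest reply is that the plan already captures what matters clinically. FPE abnormalities after injection and clinically significant ECG, laboratory and vital-sign changes become AEs. AE tables are organised by system organ class and preferred term, not by visit, and suspected toxin-spread and hypersensitivity events have their own tables (SAP 2.5.2.2). TEAEs are defined by onset time (SAP 1.5.1). The readings themselves are listed. Most of the affected tables are by-visit tables by design, and Protocol 8.2 prescribes no ECG or blood sample at an unscheduled visit, so there may be few such readings or none.

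All of this stands, and it rules out several stronger readings that one might infer:
- *That event-driven findings disappear from the safety evidence.* They do not. The AE route and the listings hold them.
- *That most of follow-up is excluded.* The 140-day gap describes the assessment schedule, not data removed by the SAP.
- *That the bias favours the more toxic arm.* This would need unequal AE-driven visits between arms, tests done at them, and abnormal results not counted elsewhere. None is shown.
- *That AEs found at unscheduled visits go uncounted.* The words of SAP 2.1.1 could be read so, but the structure of SAP 2.5.2 points the other way.

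The reply does not dispose of the readings that miss the AE route. Listings give no count by arm. Table 14.3.12.3 is not labelled as by-visit, and nothing in the SAP brings unscheduled readings back into it.

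**Conclusion.** The concern holds in a limited form. As written, SAP 2.1.1 leaves unscheduled readings that are not judged clinically significant out of every by-arm count. It also allows the FPE and ECG tables to disagree with the AE tables. This follows from the text and needs no assumption.

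The size is unknown. Each affected subject is worth 0.85 points in an active arm or 1.69 in placebo, which would be visible for a rare category such as QTc above 500 msec, but the number of such subjects may be small or nil. Any bias between arms depends on unequal AE-driven visits. The primary analysis and the AE tables, read in the natural way, are unaffected. The correction is cheap and worth making, but the gap does not put the safety conclusion in doubt by itself.

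**What to change.** 1. In SAP 2.1.1, limit the exclusion to efficacy analyses and to by-visit summaries.
2. Add an any-post-baseline (worst value) row that includes unscheduled post-treatment readings. Apply it to the QTcF/QTcB threshold and change categories, the ECG overall-assessment shift, Table 14.3.12.3, the FPE shift, and minimum and maximum laboratory and vital-sign values.
3. State that AEs are counted whatever visit they are reported at.
4. Beside the new row, give the number of subjects per arm who contribute an unscheduled reading. More readings mean more chances to cross a limit, and the reader needs this count to interpret a difference between arms.

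The cost is a few sentences and one extra row in some safety tables; by-visit results do not change. Abnormality percentages in the new row will be slightly higher. As the SAP is already in effect, the change would be documented in the clinical study report, as Protocol 9.1 and SAP 2.1 require.

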2.1.2 Pooling of Centers

As this is a multi-center study, it is possible that some sites may only enroll a small number of subjects. Since this study plans to conduct some site-level analyses, pooling of sites may need to be considered for reliable and accurate results. If any site enrolls less than 5 subjects, then sites will be pooled by the following geographic regions:

- US sites
 - East
 - North
 - South

 GALDERMA	Title 43QMI902 Statistical Analysis Plan US - QMI114-DP - GL&LCL	Doc id MA-43265
--	---	----------------------------------

Effective date: 2021-02-05 13:16

Effective

Version: 1.0

- West
- Canadian sites
 - If only one site exists in this country, then its region will be pooled with the respective US region above (i.e. Canada – East will be pooled with US – East); otherwise sites will be pooled into the following geographic regions:
 - East
 - North
 - South
 - West

This region-level site grouping will then be used for all site-level analyses. This will be done prior to unblinding.

2.2 Analysis Populations

The statistical analyses will be performed based on the following four subject populations:

- Modified Intent-to-Treat efficacy population – The modified Intention-to-treat (mITT) population includes all subjects who are randomized and dispensed the investigational product, and will be analyzed according to the randomization scheme; subjects with a photographic and categorical scale Month 1 assessment via a remote visit will be excluded from the mITT.
- Intention-to-treat efficacy population - The Intention-to-treat (ITT) population includes all subjects who are randomized and dispensed the investigational product and will be analyzed according to the randomization scheme.
- Per-protocol efficacy population - The Per-protocol (PP) population is a subset of the mITT subjects who have no protocol deviations that are considered to have a substantial impact on the primary efficacy outcome.
- Safety population - The safety population includes all subjects who were administered the study product and will be analyzed according to as-treated principle.

2.3 Study subjects

2.3.1 Subject disposition

Subject disposition will be presented by treatment group and overall. The number of subjects in each study population (i.e. mITT, ITT, PP and Safety) will be summarized. Study population variables will also be presented in a data listing. Study completion, as well as early discontinuation, will be described for all subjects as well as by visit and by center.

Reasons for early discontinuation will be summarized and listed. All withdrawn subjects will be listed individually, including at least subject number, date and reason for withdrawal, and last visit performed, along with the relevant comments recorded on the eCRF (i.e., the Exit Form).

2.3.2 Protocol deviations

A protocol deviation occurs when a subject deviates from the protocol procedures. Depending on the seriousness of the deviation, the subject might be excluded from the PP analysis. Since PP will be used for the primary analysis at Month 1 only, the focus will be on deviations occurring before and on Month 1 visit day, as they might compromise the primary endpoint.

2021-02-05 13:16

Effective date:

Effective

Version: 1.0

For this study, the protocol deviations that will exclude subjects from PP are identified in (but not limited to) Table 3 below.

Table 3. Protocol deviations

Deviation
Any subject that conducts their Month 1 visit out of window by greater than 14 days or earlier than 7 days
Any subject not treated according to the assigned treatment
Any subject that does not complete the GL-ILA at maximum frown at the primary endpoint visit (Month 1)
Any subject that does not complete the GL-SLA at maximum frown at the primary endpoint visit (Month 1)
Any subject that does not complete the LCL-ILA at maximum smile at the primary endpoint visit (Month 1)
Any subject that does not complete the LCL-SLA at maximum smile at the primary endpoint visit (Month 1)
Any subject that does not have an available screening or baseline GL-ILA at maximum frown assessment
Any subject that does not have an available screening or baseline GL-SLA at maximum frown assessment
Any subject that does not have an available screening or baseline LCL-ILA at maximum smile assessment
Any subject that does not have an available screening or baseline LCL-SLA at maximum smile assessment
Any subject that does not have grade 2 or 3 at maximum frown on the GL-ILA at baseline
Any subject that do not have grade 2 or 3 at maximum frown on the GL-SLA at baseline
Any subject that does not have grade 2 or 3 at maximum smile on the LCL-ILA at baseline
Any subject that do not have grade 2 or 3 at maximum smile on the LCL-SLA at baseline
Any subject with prohibited concomitant treatments/procedures prior to Month 1 visit considered to have a substantial impact on the primary efficacy outcome.
Any subject with a prohibited medical history, unstable medical history condition, or medical history condition that worsens prior to Month 1 visit considered to have a substantial impact on the primary efficacy outcome

Before unblinding the subject data, and as a part of preparations for the database lock, the study team will review all protocol deviations. All protocol deviations will be presented in a data listing.

Handling of Protocol Deviations During COVID-19

Due to the public health emergency related to the COVID-19 pandemic during 2020, steps have been taken to ensure patient and practitioner safety in alignment with FDA Guidance dated May 11, 2020 (Guidance on Conduct of Clinical Trials of Medical Products during COVID-19 Public Health Emergency). Most notably, in partnership with clinical sites and the Institutional Review Board (IRB), optional remote assessment procedures for efficacy and safety endpoints have been implemented to ensure safety and respect localized and elective restrictions.

Protocol deviations will be presented descriptively, overall and by treatment group. The total number of deviations, the type of protocol deviation, and if the deviation was reportable to the IRB

	Title 43QMI902 Statistical Analysis Plan US - QM1114-DP - GL&LCL	Doc id MA-43265
--	---	----------------------------------

will be summarized. These summaries will be stratified by relatedness to COVID-19 (related, not related). The above summary of protocol deviations will be repeated by site as well.

A listing of all protocol deviations reported throughout the study, including their relatedness to COVID-19, will be provided.

2.3.3 Demographic characteristics

Demographic assessments for this study include:

- Age (years)
- Height (in)
- Weight (lbs.)
- BMI (kg/m²)
- Gender (Male, Female)
- Ethnicity (Hispanic or Latino, Not Hispanic or Latino)
- Race (White, Black or African American, Asian, American Indian or Alaska Native, Native Hawaiian or Other Pacific Islander, Other)
- FST score (I, II, III, IV, V, VI)
- Prior use of botulinum toxin (Naive, Non-Naive)

Subject demographic data will be summarized for the ITT population by treatment group and overall. Age, height, weight, and BMI will be analyzed as continuous variables. Gender, race, ethnicity, Fitzpatrick skin type, and prior botulinum toxin use status will be analyzed as categorical variables.

Demographics and baseline characteristics will be presented by subject in a data listing.

2.3.4 Medical history and previous/concomitant medication (including drugs and medical and surgical procedures)

All summaries will be done by treatment group based on the ITT population. History of relevant or clinically significant surgical events and medical conditions, including any prior cosmetic/aesthetic procedures or implants, will be collected. Medical History will be coded according to MedDRA; the version used will be noted as a footnote in the tables and listings.

The number and percentage of subjects reporting medical history will be summarized by system organ class (SOC) and preferred term (PT). System organ class and PTs will be presented in descending frequency first based on the QM1114-DP in GL/QM1114-DP in LCL group, and then alphabetically if there are ties. Each subject will contribute at most one count per summarization category. In other words, if a subject has more than one medical history event with same PT, the subject will be counted only once for that PT. Similarly, if a subject has more than one medical history event for a SOC, the subject will be counted only once in that SOC.

Cosmetic/aesthetic procedures and/or implant history will also be presented and will follow the same methods specified above.

Medical history, and prior cosmetic/aesthetic procedures or implants will be provided in the subject data listing. Medical history will be further presented in a separate listing by past and ongoing GL and LCL medical history.

 GALDERMA	Title 43QMI902 Statistical Analysis Plan US - QM1114-DP - GL&LCL	Doc id MA-43265
--	---	----------------------------------

Effective date: 2021-02-05 13:16

Effective

Version: 1.0

Concomitant medications for this study are defined as any ongoing medications with a start date prior to the date of injection, any changes to existing medications (such as dose or formulation) during the course of the study, or any new medications received by the subject since the date of injection. Prior medications are medications with stop dates prior to study treatment and used within 4 weeks preceding screening visit. Medications will be coded using the World Health Organization (WHO) Drug Dictionary, concomitant procedures will be coded according to MedDRA. The versions used for the coding will be noted as a footnote in the tables and listings.

The number and percentage of subjects who receive prior and concomitant medications will be summarized by the WHO Drug Dictionary Anatomical Therapeutic Chemical 3rd level (ATC-3) and the preferred name. If the 3rd level term is not available, the next available level (e.g., ATC-2) will be used. In addition, the number and percentage of subjects reporting a concomitant medication/therapy will be summarized by reason (medical history, adverse event, concomitant procedure, contraception, or other). Therapies and procedures that started due to an AE will be summarized separately from those who did not start due to an AE.

ATC-3 and preferred name will be presented in descending frequency first based on the QM1114-DP in GL/QM1114-DP in LCL group, and then alphabetically if there are ties. Each subject will contribute at most one count per summarization category. In other words, if a subject has more than one medication with same preferred name, the subject will be counted only once for that preferred name. Similarly, if a subject has more than one medication for an ATC-3 level, the subject will be counted only once in that ATC-3 level and preferred name. Concomitant procedures will also be presented and will follow the same methods specified for medical history.

Prior and concomitant medications/procedures will be presented by subject in a data listing.

Handling of Missing/Partial Dates

While every effort will be made to obtain full, complete information on every reported medication, the following imputation rules will be followed for any respective missing medication data:

For the purpose of determining whether a medication is considered prior or concomitant, the following date imputation rules will be used. Dates will be presented as collected in the listings.

- Start Date
 - If the start date is completely missing, it will be assumed that the medication started on the study treatment date.
 - If the start date is missing the day, the first of the month will be used (i.e. UNK-JAN-2019 becomes 01-JAN-2019), provided the imputed date is on or after the subject's study treatment date; otherwise, the day of study treatment will be used.
 - If the start date is missing the month, the month of 'June' will be used (i.e. 01-UNK-2019 becomes 01-JUN-2019), provided the imputed date is on or after the subject's study treatment date; otherwise, the subsequent month after study treatment will be used.
 - If the start date is missing the year, the year of study treatment will be used (i.e. 01-JAN-UNK becomes 01-JAN-2019), provided the imputed date is on or after the subject's study treatment date; otherwise, the subsequent year after treatment will be used.
- End Date

 GALDERMA	Title 43QMI902 Statistical Analysis Plan US - QM1114-DP - GL&LCL	Doc id MA-43265
--	---	----------------------------------

2021-02-05 13:16

Effective date:

Effective

Version: 1.0

- If the end date is completely missing, it will be assumed that the medication is still ongoing and will not be imputed.
- If the end date is missing the day, the last day of the month will be used (i.e. UNK-JAN-2019 becomes 31-JAN-2019).
- If the end date is missing the month, the subsequent month after the start date will be used.
- If the end date is missing the year, the year of study treatment will be used (i.e. 01-JAN-UNK becomes 01-JAN-2019), provided the imputed date is after the start date; otherwise, the subsequent year after start date will be used.

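### The medication start-date rule in SAP 2.3.4 overrides recorded pre-treatment starts, which can put a start after its stop and, when the stop lacks its year or month, can push that stop past injection.

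*SAP*

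**What the plan says.** SAP 2.3.4, under its paragraph on missing and partial dates, gives the aim of the rules: "For the purpose of determining whether a medication is considered prior or concomitant". For starts it has four rules:

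- Nothing recorded: "If the start date is completely missing, it will be assumed that the medication started on the study treatment date".
- Day missing: the 1st of the month, if that is not before treatment; "otherwise, the day of study treatment will be used".
- Month missing: June, if that is not before treatment; "otherwise, the subsequent month after study treatment will be used".
- Year missing: the treatment year, if that date is not before treatment; "otherwise, the subsequent year after treatment will be used".

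For stops, a missing day becomes the last day of the month and a wholly missing stop means ongoing. For a missing month the rule is: "If the end date is missing the month, the subsequent month after the start date will be used". A missing year becomes the treatment year if the resulting date is later than the start, and otherwise the year following the start.

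The same section defines prior medication by a stop before treatment together with use in the 4 weeks before screening. Concomitant medication is ongoing medication that began before injection, changed medication, or medication new since injection. Listings show dates as collected.

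**The concern.** A medication, unlike a treatment-emergent event, can properly begin before injection. The start rules nevertheless replace any imputed date that falls before treatment, with no exception for a recorded month and year that already settle the matter. SAP 2.5.2 uses the same floor for adverse events, where it serves treatment emergence. The SAP gives no reason for applying it to medications, and it sits badly with the definition of concomitant medication that turns on a start before injection.

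Two things follow. The derived interval can be impossible, with the start after the stop. And because two of the stop rules refer back to the start, a moved start can carry a stop past injection and change the class. At stake is whether the prior and concomitant medication tables count the right subjects for incompletely dated records.

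**Working it through.** **Inputs.** The start rules, stop rules and class definitions are in SAP 2.3.4. Protocol 8.1.1 allows at most 14 days from screening to baseline. Protocol Table 2 defines a month as 28 days. The documents give no subject's treatment date, so 05-AUG-2020 is an assumption; the pattern needs only a recorded start month before treatment.

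**The plan's own examples.** Applied literally, the rules turn UNK-JAN-2019 into 01-JAN-2019 only if treatment is on or before 01-JAN-2019, and 01-UNK-2019 into 01-JUN-2019 only if treatment is on or before 01-JUN-2019. For later treatment dates the printed results do not arise.

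**Moved start.** For UNK-MAY-2020, the 1st of the month is 01-MAY-2020. This precedes 05-AUG-2020, so the start becomes 05-AUG-2020.

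**Result by type of stop**, taking the start in the stop rules to be the imputed one:

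| Recorded stop | Stop with moved start | Class by stop | Stop if 01-MAY-2020 is kept | Class by stop |
|---|---|---|---|---|
| 20-JUL-2020 | 20-JUL-2020 | prior | 20-JUL-2020 | prior |
| UNK-JUL-2020 | 31-JUL-2020 | prior | 31-JUL-2020 | prior |
| 20-JUL-UNK | 20-JUL-2021 | concomitant | 20-JUL-2020 | prior |
| 20-UNK-2020 | 20-SEP-2020 | concomitant | 20-JUN-2020 | neither |
| missing | ongoing | concomitant | ongoing | concomitant |

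- Row 1: the imputed start is 11 + 5 = 16 days after the stop. The class by stop date does not change.
- Row 3: 20-JUL-2020 is not later than 05-AUG-2020, so the year after the start is used. Month 6 is 6 × 28 = 168 days after treatment, which is 20-JAN-2021, or 25-JAN-2021 with the 5-day window. A stop on 20-JUL-2021 therefore lies beyond study exit, and with a May 2020 start the only date that fits is 20-JUL-2020. That date is also in the 4 weeks before screening: permitted screening runs from 22-JUL to 05-AUG-2020, so the window opens between 24-JUN and 08-JUL-2020. The drug is prior and would be tabulated as concomitant.
- Row 4: the moved start again carries the stop past injection, but this is not prior medication misclassified. 20-JUN-2020 precedes 24-JUN-2020, the earliest opening of the window, so the record would fall in neither table. The true stop month is unknown, and concomitant may be right.

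**Other start patterns.** 01-UNK-2019 moves to September, the month after treatment. The rule does not say whether 2019 is kept; if the year moves too, the result is 01-SEP-2020. 01-JAN-UNK becomes 01-JAN-2021, but a start with no recorded year is not known to precede treatment.

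**Second assumed treatment date, 15-JUN-2020.** UNK-MAY-2020 with stop 05-JUN-2020 gives a start 10 days after the stop. UNK-APR-2020 with stop 01-JUN-UNK gives 15-JUN-2020 to 01-JUN-2021, where keeping April gives 01-APR-2020 to 01-JUN-2020. The pattern is the same.

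**The case against.** A reader might infer that pre-treatment medication is generally misclassified as concomitant. The SAP does not support that. Prior status turns on the stop date, so a complete or day-missing pre-treatment stop keeps the drug prior, and a missing stop makes it concomitant whatever the start. Only an incomplete start combined with a stop lacking its month or year can change class on the stop-date test. This part of the objection stands. One gap remains: a program that instead tests whether the start is on or after injection would call the row 1 record new since injection, and the SAP states no order of precedence.

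The link between stop and moved start is also a reading. The stop rules refer to the start date without saying that it is the imputed one. If the recorded parts were used, May 2020 would already precede 20-JUL-2020 and the 2021 stop would not arise. The imputed date is the natural reading, because a rule that needs a month or a comparison needs a usable date, but the text should say so.

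The impossible intervals appear in no planned output. Listings show collected dates, the medication tables count subjects by drug class and name, and no medication onset or duration is summarised. That also stands and limits the harm to classification.

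A reader might further infer that subjects could wrongly leave the per-protocol population, since prohibited treatment before Month 1 is an exclusion in SAP 2.3.2, Table 3. That exclusion requires a judged substantial impact on the primary outcome, and the study team reviews all deviations before unblinding. SAP 2.3.4 limits the imputation to the prior/concomitant class. Nothing says that imputed dates feed the deviation review.

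**Conclusion.** The point holds in limited form. It is certain that the missing-day rule overrides a recorded pre-treatment month and year, and that no start rule checks the recorded stop, so a start can follow its stop. A stop lacking its year can turn medication stopped before injection into concomitant medication, provided the stop rules use the imputed start. A stop lacking its month is also carried past injection, but whether that is wrong depends on a month nobody recorded.

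The effect is confined to the descriptive Tables 14.1.7.x. The documents give no count of incompletely dated records; it is probably small. No per-protocol or primary-analysis effect is shown. This is a minor correction, worth making because it is cheap. The worked dates rest on assumed treatment dates.

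**What to change.** Amend SAP 2.3.4 as follows.

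1. Move a partial start to the treatment date only when its recorded parts are compatible with a start on or after treatment and the stop does not precede treatment. Otherwise use the earliest date consistent with the recorded parts.
2. Never let an imputed start exceed the recorded stop. This also settles starts with no year, or nothing, recorded when the stop is before treatment.
3. Replace the missing-month stop rule with the latest date consistent with the recorded parts, capped at study exit. Changing the start rule alone would do harm: with treatment on 05-AUG-2020, UNK-JAN-2020 / 20-UNK-2020 would become 01-JAN to 20-FEB-2020 and drop out of both tables, although use may have continued past injection. With the new stop rule the stop is 20-DEC-2020 for a subject who reaches Month 6 (20-JAN-2021), and the drug stays concomitant.
4. State that the class is decided by stop date or ongoing status.

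The cost is a short rewrite of the date rules and one derivation macro, with no new data. Protocol 9.1 requires changes to the finalized SAP to be documented in the study report.
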